8.6 Adjustments for Multiplicity

There will be no adjustment for the multiplicity of these active concentrations (0.01%, 0.02%, or 0.04%) tested against placebo in this Phase 2 study.

9. Disposition of Subjects

Subject disposition will be presented in terms of the numbers and percentages of subjects who were randomized, completed the study, and discontinued from the study. The number of subjects in each of the analysis populations (ITT, PP, and Safety) will be displayed by treatment and percentages will be calculated using randomized subjects as the denominator. Subjects who are not discontinued from the study will be considered study completers. Disposition will be summarized by treatment group and for all subjects. Subject listings of disposition will be produced for all randomized and screen failed subjects separately.

The number and percentage of subjects prematurely discontinued from the study and the reasons for study discontinuation will be summarized by treatment group for all randomized subjects. The reasons for study discontinuation that will be summarized include: AE, withdrawal of consent, non-compliance,

lost to follow-up, lack of efficacy, disallowed concurrent medication, investigator decision, protocol violation, death, and an “other” category for reasons other than those previously listed. Each subject will have the single, primary reason for study discontinuation captured and summarized. The denominator for calculating the percent of subjects discontinuing the study for each reason will be the total number of discontinued subjects in the treatment group.

The number and percentage of subjects with protocol deviations (any deviations, major deviations, and minor deviations) will be summarized by treatment group for all randomized subjects. A subject listing will be provided that includes the date of the deviation, the deviation description, the deviation code, the classification of whether the deviation was judged to be major or minor, and whether the subject is included in the PP population. A separate listing for inclusion not met/exclusion met for screen failures will also be produced.

10. Demographic and Pretreatment Variables

10.1 Demographic and Baseline Characteristics Variables

Demographic and baseline characteristics will be summarized by treatment group for the ITT population. The demographic variables will include age and sex.

Age (years) will be summarized, overall and by treatment, using continuous descriptive statistics. Age will also be categorized as follows: <65 years and ≥65 years. Age will be reported in years and calculated using the following formula:

$$\text{Age} = (\text{Informed Consent Date} - \text{Date of Birth}) / 365.25, \text{ truncated as an integer}$$

Baseline characteristics will include study eye diagnosis of OHT or OAG, length of time since study eye diagnosis of OHT or OAG (weeks), prior hypotensive therapy, time on prior hypotensive therapy (weeks), study eye IOP at screening visit (Visit 1), and study eye mean diurnal IOP on Day 1 (Visit 3). Additionally, visual field mean deviation, central corneal thickness, and cup-to-disc ratio at screening visit will be summarized separately for study eye and fellow eye.

Test of differences between each of the active treatment group and placebo will be performed for demographic and baseline characteristics variables. Analysis of variance (ANOVA) will be employed to assess differences between treatments for continuous variables. Fisher’s exact test will be used to assess differences between treatments for categorical variables.

A subject listing that includes all demographic and baseline characteristics variables will be provided. Separate listings of childbearing potential responses for female subjects, visual field exams, central corneal thickness will also be produced.

10.2 Pretreatment Variables

All pretreatment variables will be included along with their respective post-treatment variables in the relevant summaries and listings.

10.3 Visual Function Questionnaire (VFQ-25)

The VFQ-25 is a reliable and valid 25-item version of the 51-item National Eye Institute Visual Function Questionnaire that measures subjective assessment of patient-reported vision-targeted health status elements that are most important to people with eye disease. All subjects will undergo VFQ-25 at Visit 3 (Qualification #2, Day 1, 09:00) in the treatment period. For observational period, the VFQ-25 data will be collected at OBS Visit 1 and Final Visit.

The VFQ-25 sub-scale scores and composite score will be calculated as the steps below.

Table 15-1 Step 1: Recoding of Items

Question Numbers	Original Item Score ^(a)	Recoded Value
1, 3, 4, 15c ^(b)	1	100
	2	75
	3	50
	4	25
	5	0
2	1	100
	2	80
	3	60
	4	40
	5	20
	6	0
5, 6, 7, 8, 9, 10, 11, 12, 13, 14, 16, 16a, A3, A4, A5, A6, A7, A8, A9	1	100
	2	75
	3	50
	4	25
	5	0
	6	*
17, 18, 19, 20, 21, 22, 23, 24, 25, A11a, A11b, A12, A13	1	0
	2	25
	3	50
	4	75
	5	100
A1, A2	0 to 10	0 to 10

^(a)Precoded response choices as printed in the questionnaire.

^(b)Question 15c has four-response level, but is expended to a five-levels using question 15b.

Note: If 15b=1 then 15c should be recoded to 0.

If 15b=2, then 15c should be recoded to missing.

If 15b=3, then 15c should be recoded to missing.

*Response choice "6" indicates that the person does not perform the activity because of non-vision related problems. If this choice is selected, the item is coded as "missing".

Table 15-2 Step 2: Averaging Items to Generate VFQ-25 Sub-Scales

Sub-Scale	Number of items	Items to be averaged (after recoding per Table 15-1)
General Health	1	1
General Vision	1	2
Ocular Pain	2	4, 19
Near Activities	3	5, 6, 7
Distance Activities	3	8, 9, 14
Vision Specific:		
Social Functioning	2	11, 13
Mental Health	4	3, 21, 22, 25
Role Difficulties	2	17, 18
Dependency	3	20, 23, 24
Driving	3	15c, 16, 16a
Color Vision	1	12
Peripheral Vision	1	10

The subject's sub-scale score is the average of scores from non-missing items. The higher scores indicate better vision-specific health-related quality of life. The subject's composite VFQ-25 score is the average of all sub-scale scores except for the general health item.

The VFQ-25 sub-scale scores and composite score will be summarized using the continuous summary statistics for Visit 3.

A subject listing of VFQ-25 sub-scale and composite scores will also be produced.

10.4 Contrast Sensitivity Testing

Contrast sensitivity charts will be used to assess visual function. All subjects will have a CS testing at Visit 3 in the treatment period. In the observational period, the CS data will be collected at OBS Visit 1 and Final Visit.

The CS results will be summarized at eye level using the discrete summary statistics for each spatial frequency by treatment group. The numeric part of the CS results will be summarized using continuous summary statistics.

A subject listing of CS testing will also be produced.

11. Medical History and Concomitant Medications

11.1 Medical History

Significant medical history will be collected and any current underlying medical conditions, including those that began within the last 30 days and which may have resolved before screening, must be recorded. Medical history will be coded using the Medical Dictionary for Regulatory Activities in Japanese (MedDRA/J), Version 21.1.

Ocular and non-ocular medical history will be summarized separately using discrete summary statistics by treatment group at the subject level by System Organ Class (SOC) and Preferred Term (PT) using the safety population. If a subject reports the same PT multiple times within the same SOC, that PT will

only be reported once within that SOC. As with the PT, if a subject reports multiple conditions within the same SOC, that SOC will only be reported once.

Additionally, glaucoma history will be summarized similarly to ocular history.

Listings of medical history will be generated separately for ocular and non-ocular data. Listing of ocular surgery/laser procedures will also be produced.

11.2 Prior and Concomitant Medications

Use of all medications will be documented on the appropriate CRF. Prior and concomitant medications will be coded using the World Health Organization (WHO) Drug Dictionary (Global, B3, September 2018) and summarized to the therapeutic drug class (Anatomical Therapeutic Chemical [ATC] 4 classification) and preferred name. If the ATC 4 classification is not provided, the next lowest classification that is provided in the coding dictionary will be used. The preferred name will be defined as the active ingredient; if the active ingredient is not provided or includes more than two ingredients (eg, multivitamins) then the drug name will be summarized as the preferred name.

Concomitant medications will be summarized separately for ocular and non-ocular data using the safety population. Medications will be tabulated for each treatment group using frequencies and percentages. Subjects may have more than one medication per ATC text. At each level of subject summarization, a subject will be counted once if he/she reports one or more medications.

Listings of prior and concomitant medications will be generated separately for ocular and non-ocular data. Listing of washout medication will also be produced.

12. Dosing Compliance and Treatment Exposure

12.1 Dosing Compliance

Dosing compliance is calculated as: $100 * (\text{Number of Actual Dosing Days}) / (\text{Number of Expected Dosing Days})$. Dosing compliance will be summarized with continuous descriptive statistics for each treatment group, using the safety population.

12.2 Treatment Exposure

Extent of treatment exposure for completed or discontinued subjects will be calculated in days using the following:

$$\text{Extent of Exposure (days)} = (\text{Date of Last Dose} - \text{Date of Visit 3}) + 1$$

Extent of treatment exposure (days) for each subject exposed to study drug will be summarized with continuous descriptive statistics for each treatment group, using the safety population.

A subject listing of study drug administration will also be produced.

13. Efficacy Analyses

13.1 Primary Efficacy Analysis

The primary efficacy endpoint will be the mean of mean diurnal IOP at Week 4 (Day 29). The primary analysis of the primary endpoint will employ an analysis of covariance (ANCOVA) model with mean of mean diurnal IOP at Week 4 as the response, baseline mean of mean diurnal IOP as a covariate, and treatment as a main effect, using the ITT population with MCMC multiple imputation techniques used to impute missing data. The least squares (LS) mean differences (netarsudil – placebo) will be presented separately for netarsudil 0.01%, 0.02%, and 0.04% as well as two-sided p-values and 95% CIs. For a given comparison, if the p-value is <0.05 and the point estimate of the LS mean difference is < 0, then the netarsudil group will be considered superior to the placebo.

The following SAS code will be used for multiple imputations using the MCMC method:

```
proc mi data = inidata seed = 48669 out = outdata1;
  mcmc initial = em;
  var trt01pn baseline IOP;
  run;
  where
    - inidata is the name of the input dataset
    - outdata is the name of the output dataset
    - trt01pn is the name of the treatment group variable in numeric format
    - baseline is the corresponding baseline IOP for a given time point
    - IOP is the name of the IOP measure.
```

Five (5) complete data sets will be generated from the above code. Each complete data set will be used to analyze this primary efficacy endpoint separately using ANCOVA. Then, the SAS procedure MIANALYZE will be used to analyze the results from the 5 complete data sets to generate a combined inference. The following SAS code will be used:

```
ods output diffs = outdata2;
proc mixed data = outdata1;
  class trt01pn;
  model IOP = trt01pn baseline;
  lsmeans trt01pn / cl pdiff;
```

```

by _Imputation_;
run;

proc sort data = outdata2;
  by trt01pn trt01pn;
run;

ods output ParameterEstimates = outdata3;

proc mianalyze data = outdata2 alpha = 0.05;
  by trt01pn trt01pn;
  modeleffects estimate;
  stderr stderr;
run;

```

where

- *IOP* is the name of the IOP measure
- *trt01pn* is the name of the treatment group variable in numeric format
- *outdata2* is the name of the output dataset that contains the statistical results of the differences between treatment groups
- *outdata3* is the name of the output dataset that contains summary and inferential statistics.

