4. STUDY POPULATION SELECTION

4.1 Study Population

A total of approximately 208 Japanese subjects will be enrolled in this study at approximately 30 investigational sites in Japan comprising a total of 52 subjects per treatment arm for each of the 4 treatment arms. Subjects will be at least 20 years of age with diagnosed OAG or OHT, each of whom meets all inclusion criteria and none of the exclusion criteria.

Planned enrollment numbers are higher (208 total, 52 subjects per arm) than statistically required for demonstrating efficacy (approximately 49 intent-to-treat [ITT] subjects per arm for 90% power) to account for the potential for subjects who do not complete the entire dosing period, or who have disqualifications. Over-enrollment (beyond 208 subjects) is to be undertaken only after communication between the investigational site and the Sponsor representative.

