5.4 Method of Assigning Patients to Treatment Groups

A randomization code for allocating the treatments will be prepared by an independent biostatistician who is not involved in the day-to-day conduct of the study. Subjects will be randomized using IWRS in a 1:1:1:1 ratio to receive netarsudil ophthalmic solution (0.01%, 0.02% or 0.04%) or its placebo and will stratify subjects by site.

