9.5.2 Primary Efficacy Analyses

The primary analysis of the primary endpoint will employ a linear model with mean diurnal IOP at Week 4 as the response, baseline mean diurnal IOP as a covariate, and treatment as a main effect factor, using the ITT population with Monte Carlo Markov Chain multiple imputation techniques used to impute missing data. The least squares mean differences (netarsudil – placebo) will be presented separately for netarsudil 0.01%, 0.02% and 0.04% as well as 2-sided p-values and 95% confidence intervals (CIs). Inference will be made on the 2-sided p values. Superiority for a concentration (0.01%, 0.02% and 0.04%) will be concluded if the 2-sided p-value, for testing the difference (netarsudil – placebo) to 0, ≤ 0.05 and the point estimate of the difference < 0 at Week 4 for that concentration.

There will be no adjustment for the multiplicity of the 3 active concentrations (0.01%, 0.02% and 0.04%) tested against placebo in this Phase 2 study.

Analyses will be performed primarily on the ITT population using multiple imputation techniques to impute missing data. Sample SAS code to demonstrate the methodology that will be used for data imputation can be found in [Appendix 6](#).

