Appendix 6 Sample SAS Code

The following SAS code will be used for multiple imputations using the Monte-Carlo Markov Chain method, where a separate model will be fit for each time point at each visit.

```
proc mi data = indata seed = 6876 out = outdata1;  
  
mcmc initial = em;  
  
var trt01pn baseline IOP;  
  
run;
```

where

- *indata* is the name of the input dataset
- *outdata1* is the name of the output dataset
- *trt01pn* is the name of the treatment group variable in numeric format
- *baseline* captures the baseline IOP for the given time point
- *IOP* is the name of the IOP measure.

Thirty complete data sets will be generated from the above code. Each complete data set will be used to analyze this primary efficacy endpoint separately using analysis of variance. Then, the SAS procedure MIANALYZE will be used to analyze the results from the 30 complete data sets to generate a combined inference. The following SAS code will be used:

```
ods output diffs = outdata2;  
  
proc mixed data= outdata1;  
  
by _IMPUTATION_;  
  
class trt01pn;  
  
model IOP = trt01pn baseline;  
  
lsmeans trt01pn / cl pdiff;  
  
run;  
  
proc sort data= outdata2;  
  
by trt01pn _trt01pn;
```

```
run;  
  
ods output ParameterEstimates = outdata3;  
  
proc mianalyze data= outdata2 alpha = 0.05;  
    by trt01pn _trt01pn;  
    class trt01pn _trt01pn;  
    modeleffects estimate;  
    stderr;
```

run;

where

- *outdata1* is the name of the input dataset from Proc MI
- *_IMPUTATION_* is the imputation number
- *trt01pn* is the name of the treatment group variable in numeric format
- *IOP* is the name of the IOP measure
- *baseline* captures the baseline IOP for the given time point
- *outdata2* is the name of the output dataset that contains the statistical results of the difference between treatment groups
- *outdata3* is the name of the output dataset that contains summary and inferential statistics.

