4.1 Method of Assigning Subjects to Treatment Groups

A randomization code for allocating the treatments will be prepared by an independent biostatistician who is not involved in the day-to-day conduct of the study. Subjects will be randomized using IWRs in a 1:1:1:1 ratio to receive netarsudil ophthalmic solution (0.01%, 0.02% or 0.04%) or its placebo and will be stratified by site.

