4.2 Masking

Treatment assignments will be masked to the Investigator, the clinical study team (Sponsor, personnel involved in day to day study management, Monitors, Data Managers, and Statisticians), and the subjects for the duration of the study. Only in case of medical emergency or occurrence of AEs that warrant unmasking in the opinion of the Investigator, will the treatment assignment(s) be unmasked and made available to the Investigator and the Sponsor Medical Monitor or designee. Individual unmasking by the Investigator will normally result in withdrawal of the subject from the study and should only be performed for the specific subject requiring unmasking. In the absence of medical need, the randomization code will not be available to the above personnel until after the study is completed and the database is unlocked.

5. Sample Size and Power Considerations

Assuming a two-sided test with alpha = 0.05, a common standard deviation (SD) of 3.5 mmHg at each time point yielding a common SD of 3.0 for the diurnal mean, and a correlation among time points of 0.60, 49 intent-to-treat (ITT) subjects per arm yields at least 90% power to demonstrate superiority of netarsudil (0.01%, 0.02%, or 0.04%) to placebo in mean diurnal study eye IOP (average of 09:00, 11:00, and 16:00 hours) at the Week 4 visit assuming a difference of at least 2.0 mmHg in the mean diurnal IOP. Accounting for approximately a 5% discontinuation rate, 52 subjects per arm (208 total) will be enrolled.

6. Data Preparation

Study data will be recorded via electronic case report forms (eCRF). Each authorized study staff member will receive a unique access account in order to use the Electronic Data Capture (EDC) system. Access accounts will not be shared among study staff. Authorized users will make entries and/or changes to the eCRFs via a secure internet access. Each completed set of eCRFs will be reviewed by the Investigator

who will then electronically sign and date the eCRF confirming that data for the subjects are complete and accurate.

Final analyses outlined in this document will be carried out after the following have occurred:

- All data management requirements are met according to [REDACTED] standard operating procedures, including data entry, performance of edit and validation checks, documentation and resolution of data queries, and database lock with written authorization provided by appropriate [REDACTED] and Sponsor personnel.

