13.2 Secondary Efficacy Analyses

Secondary analyses of the primary efficacy endpoint include repeating the primary analysis strategy using observed data only, and LOCF where LOCF will be performed using time-relevant measures. These analyses will also be repeated on the PP population to determine robustness of results.

Additionally, secondary analyses of the primary endpoint will be completed using the two-sample t-test and 95% t-distribution CIs on the difference (netarsudil (0.01%, 0.02%, and 0.04%) - placebo) for each comparison.

The secondary efficacy endpoints include:

- Mean of Mean diurnal IOP at Weeks 1 and 2 (Days 8 and 15, respectively)
- Mean change from baseline in mean diurnal IOP at each post-treatment visit
- Mean percent change from baseline in mean diurnal IOP at each post-treatment visit

- Mean IOP at each post-treatment time point
- Mean change from diurnally-adjusted baseline IOP at each post-treatment time point
- Mean percent change from diurnally-adjusted baseline IOP at each post-treatment time point
- Percentages of subjects achieving pre-specified mean, mean change, and percent mean change in mean diurnal IOP levels

Similar ANCOVA models for primary efficacy endpoint will be used for mean of mean diurnal IOP at Weeks 1 and 2, and mean IOP at each post-treatment time point (09:00, 11:00, and 16:00 at the Week 1, Week 2, and Week 4 Visits).

Additionally, for IOP at each post-treatment time point, mixed model repeated measures (MMRM) will be run with baseline time-matched IOP as a covariate; treatment, visit, time point, treatment by visit, treatment by time point, visit by time point, and treatment by visit by time point as fixed effects; and subject as a repeated measure, using an unstructured covariance matrix. The LS mean differences (netarsudil – placebo) will be presented separately for netarsudil 0.01%, 0.02%, and 0.04% as well as two-sided p-values and 95% CIs. This analysis will be performed for the ITT population with observed data only.

Two-sample t-test and 95% t-distribution confidence intervals on the difference (netarsudil [0.01%, 0.02%, and 0.04%] - placebo) will be used for mean change from baseline in mean diurnal IOP at each post-treatment visit, mean change from diurnally-adjusted baseline IOP at each post-treatment time point, mean percent change from baseline in mean diurnal IOP at each post-treatment visit, and mean percent change from diurnally-adjusted baseline IOP at each post-treatment time point.

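### Randomization is stratified by site, but the primary Week 4 ANCOVA leaves site out and no additive site-adjusted estimate is planned; the test may be mildly conservative

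*SAP*

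**What the plan says.** **Allocation.** Protocol 5.4 assigns subjects 1:1:1:1 to a netarsudil concentration "or its placebo and will stratify subjects by site", and SAP 4.1 agrees: "or its placebo and will be stratified by site". No other stratification factor is named and no block size is given. Protocol 4.1 plans about 208 subjects at "approximately 30 investigational sites in Japan".

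**Primary model.** Protocol 9.5.2 specifies "baseline mean diurnal IOP as a covariate, and treatment as a main effect factor", and the code in Protocol Appendix 6 matches: "model IOP = trt01pn baseline". SAP 13.1 repeats this in its text ("baseline mean of mean diurnal IOP as a covariate, and treatment as a main effect") and in its PROC MIXED step. Footnote b of SAP Table 13-1 applies the same two terms to every tabulated ANCOVA. SAP 13.2 carries the model forward: "Similar ANCOVA models for primary efficacy endpoint will be used for mean of mean diurnal IOP at Weeks 1 and 2". The MMRM has no site term either.

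**Where site does appear.** SAP 13.3 lists site as a subgroup variable for Week 4 mean diurnal IOP. That model has treatment, subgroup, baseline and the treatment-by-subgroup interaction. It uses observed data only and pools sites with fewer than five subjects.

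Neither document gives a reason for leaving site out of the primary model. SAP 18 lists only the change of the p-value threshold.

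**The concern.** Balanced allocation within site removes between-site variance from the treatment contrast. A model without site leaves that variance in the residual. If site matters after baseline adjustment, the reported standard error then exceeds the true sampling SD of the estimate. Confidence intervals are wider, and p-values larger, than the design warrants.

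The planned analyses do not show whether this happens. With 208/30 = 6.9 subjects per site, or 1.7 per arm per site, the interaction model in SAP 13.3 examines heterogeneity. It gives no single site-adjusted difference per concentration, and nothing on the imputed data used for the primary inference. The other analyses of the primary endpoint (observed data, LOCF, per protocol, t-tests) change the data set or drop baseline; none adds site.

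At stake is some precision in a study whose title includes finding the optimum concentration and which judges each concentration on its own p-value. It matters most for a concentration whose true effect is below 2.0 mmHg.

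**Working it through.** **1. The plan's own figure.** SAP 5 assumes "a common standard deviation (SD) of 3.5 mmHg at each time point yielding a common SD of 3.0 for the diurnal mean", with correlation 0.60 among time points. SD of the mean of three readings = 3.5 × √((1 + 2 × 0.60)/3) = 2.997, as stated. A two-sample t-test with 49 per arm, difference 2.0, SD 3.0 and two-sided alpha 0.05 has 90.4% power, and 49/0.95 gives 52 per arm. The plan reproduces, without baseline or site adjustment.

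**2. Hand calculation with perfect balance within site.** Let ρ be the share of baseline-adjusted residual variance due to site. The documents do not give ρ, so 0 to 20% is assumed. The model uses variance 9; the contrast has variance based on 9(1 − ρ).

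- SE inflation = 1/√(1 − ρ): 1.054 at ρ = 0.10 and 1.118 at 0.20.
- Type I error = 2[1 − Φ(1.96/√(1 − ρ))]: 5.0%, 4.4%, 3.9% and 2.8% at ρ = 0, 0.05, 0.10 and 0.20.
- Power at 2.0 mmHg, 49 per arm, site-free: 2/(3√(2/49)) = 3.300, so Φ((3.300 − 1.960)/√(1 − ρ)) = 91.0%, 92.1% and 93.3% at ρ = 0, 0.10 and 0.20.
- With site in the model (noncentral t, 196 − 4 − 1 − 29 = 162 df): 90.7%, 93.3% and 95.6%. The gain is 1.2 points at ρ = 0.10 and 2.3 at 0.20.

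**3. Simulation with partial balance.** Assumed: 208 subjects, 30 sites of 1 to 23 subjects, permuted blocks of 4, residual SD 3.0, 10,000 replicates per share, averaged over the three contrasts. Monte Carlo error is at most 0.4 points on power and 0.17 on paired differences.

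| Site share | Planned SE / true SD | Type I error, planned | Type I error, random site | Power at 1.5 mmHg, planned → random site |
|---|---|---|---|---|
| 0% | 1.003 | 5.1% | 5.2% | 71.6 → 71.9% |
| 5% | 1.019 | 4.6% | 5.1% | 72.3 → 73.8% |
| 10% | 1.043 | 4.2% | 5.1% | 72.6 → 75.6% |
| 20% | 1.094 | 3.3% | 5.2% | 74.0 → 80.2% |

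At the plan's 2.0 mmHg, planned power is 92.4 to 94.1% and a random site effect adds 0.1 to 2.1 points. A separate simulation gave 0.1, 1.2 and 2.3 points at shares of 0, 10 and 20%.

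**4. Dependence on blocking.** With 196 subjects and 2,500 runs per cell (Monte Carlo error about 0.4 points), the site-free type I error at shares of 10% and 20% was 3.5% and 3.5% with blocks of 4, and 3.8% and 3.7% with blocks of 8. Without blocking it was 4.9% and 4.9%: no conservatism.

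**5. Dependence on baseline.** SD 3.0 is unadjusted. With a baseline correlation of 0.7, the residual SD is 3.0 × √(1 − 0.49) = 2.14, and the gain at 1.5 mmHg falls to 0.9 points (10% share) or 1.5 (20%). Baseline also absorbs stable site offsets. In a joint model with a raw site share of 10 to 20% and identical offsets at both visits, the residual site share is 1.6 to 6.3%. The gain at 1.5 mmHg is then 0.1 to 0.2 points (within-site correlation 0.7) or 1.1 to 1.8 (0.4). If site offsets correlate only 0.5 between visits, the residual share is 9 to 28% and the gain 1.5 to 4.6 points.

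**6. Imputation.** With the SAP's imputation variables (no site), five imputations and an assumed 5% missing at random, the random-site analysis had type I error of 4.4, 4.9 and 4.2% at shares of 0, 10 and 20% (3,000 replicates).

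**The case against.** The strongest reply is that this is a consistent, valid choice. Text and code agree across both documents, the decision rule controls error, and the power claim stands. All of that is correct.

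Three further points also stand:

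- Conservatism needs balance within site. Blocking is likely under stratified randomization, but the documents do not state it. A random site effect can still gain power without blocking, but the planned standard error is then about right.
- The larger gains use 1.5 mmHg, an effect the plan does not use. The largest also needs a 20% site share and a baseline unrelated to Week 4.
- Each subject has a same-site, three-reading baseline, which absorbs stable site differences.

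The reply that site is already analysed in SAP 13.3 stands only in part. That table is planned, but it is an interaction model on observed data and does not supply an additive adjusted difference.

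The SAP is written to protocol Amendment 2 and the protocol reviewed is Amendment 1, so a rationale could exist in text not available here.

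A reader might infer that omitting the stratification factor biases the estimates, invalidates the test or leaves the study underpowered. The documents support none of these. Nor do they show that the test is conservative in fact, since neither the site share nor the block size is given.

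**Conclusion.** A minor point, worth considering. The gap is certain: site is the only stratification factor, the primary model omits it, and no additive site-adjusted estimate is planned. The consequence is conditional. It needs site to explain Week 4 variance beyond baseline, and arms to be balanced within site. Under both conditions, type I error is about 4% at a 10% share and about 3% at 20%, and the power forgone at 2.0 mmHg and SD 3.0 is about 0 to 2 points. Site share, site sizes and block size are assumptions. Confidence is medium, because the mechanism is standard but its size here cannot be read from the documents.

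**What to change.** SAP 13.3 and the revision history in SAP 20 describe some analyses in the past tense, so the right step depends on whether treatment codes are open.

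- **Codes still masked:** add site to CLASS and `random site;` to the Week 4 PROC MIXED step as the primary model, and keep the site-free model as a sensitivity analysis.
- **Codes open:** leave the primary model unchanged. Report the random-site ANCOVA on the same imputed data sets, labelled as a sensitivity analysis, with the three differences, intervals and p-values beside the planned ones.

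The same term can be added to the Week 1, Week 2 and time-point ANCOVAs. Do not extend it to the MMRM without checking that the model converges with the unstructured covariance; that was not tested here. Do not use unpooled fixed site effects: if site is not prognostic, they cost 0.7 to 1.7 points of power at 1.5 mmHg. State in one sentence whether the imputation model includes site.

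The cost is a few lines of code, one or two SAP sentences and one extra variance component. If site is irrelevant, no power loss was measurable (type I error 5.2%; power change at 1.5 mmHg +0.1 to +0.3 points).
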